#### 1.8.1 **Pregnancy and acute opioid and ketamine use**

Limited amount of data exists from the use of sufentanil and ketamine during pregnancy. Sufentanil and ketamine crosses the placenta. There are, however, no indications to date that the use of sufentanil during pregnancy increases the risk of congenital abnormalities. The risk to the fetus can depend on various factors such as the gestational age of the pregnancy, dosage and duration of sufentanil and ketamine use.

In the current study CT001 will be used for acute pain management only and the duration of sufentanil and ketamine exposure will be very limited. Known pregnancy is a protocol exclusion criterion and the site staff will ask female participants that have reached menarche if they may be pregnant (and thus excluded). For ethical reasons it is not feasible in the ED setting to perform urine or serum pregnancy test as this would significantly delay the time to analgesia for patients in moderate to severe pain.

## 2 OBJECTIVES

### **Primary objectives:**

- To assess the safety and tolerability of CT001 in pediatric participants with moderate to severe pain in an acute care setting
- To evaluate the analgesic effect of CT001 in pediatric participants with moderate to severe pain in an acute care setting

### **Secondary objectives:**

- To assess medication errors in pediatric participants with moderate to severe pain in an acute care setting. (To be provided by site staff administering the IMP)
- To evaluate other analgesic effect of CT001 in pediatric participants with moderate to severe pain in an acute care setting.
- To evaluate the need of supplemental analgesics.
- To evaluate feasibility of CT001 in pediatric participants with moderate to severe pain in an acute care setting.

## 3 POPULATION

The study population will be recruited from children and young people aged 1 – <18 years (prior to their 18th birthday), who present to an ED following an isolated injury where immediate pain relief is judged to be needed.

### **3.1 Inclusion Criteria**

To participate in the study, and prior to performing any study-related procedures, the following inclusion criteria must all be met:

1. Participant aged 1 to <18 years.
2. Attending an ED following an injury.
3. A pain intensity score corresponding to moderate or severe pain, as assessed by age relevant scales:
  - Age group ≥9 to <18 years: pain score 5 to 10 using the Numerical Rating Scale (NRS); self-reporting by the participant.
  - Age group ≥5 to <9 years: pain score 6 to 10 using the Wong-Baker FACES scale; self-reporting by the participant.
  - Age group ≥1 to <5 years: pain score 5 to 10 using the FLACC pain scale; assessed by site staff.
4. Evidence of signed and dated informed consent form, indicating that the participant and/or parent/ guardian (if participant younger than 16 years) has been informed of and has fully understood all pertinent aspects of the study as required for the age of the child in accordance with local legislation.

### 3.2 Exclusion Criteria

To participate in the study potential participants must not meet any of the following exclusion criteria:

1. Critical, life- or limb-threatening condition requiring immediate management.
2. Open fractures.
3. Participants with chronic pain.
4. Participants requiring oxygen therapy.
5. Clinically evident respiratory depression.
6. Clinically evident cardiovascular instability (e.g. pathological arrhythmia).
7. Known liver disease.
8. Known kidney disease.
9. Presence of other acute clinical or medical condition that may, in the opinion of the investigator, put the potential subject at risk when participating in the study, impact the participant's ability to participate in the study, or have impact on the study results, including being subject to head injury and / or altered consciousness.
10. A female of childbearing potential is eligible to participate if she verbally confirms not to be at risk of being pregnant or breastfeeding and agrees to follow the contraceptive guidance for 7 days after IMP administration.
11. Acute intoxication with drugs or alcohol, based on the judgement of the attending physician.
12. Participant showing abnormal nasal cavity/airway such as:
  - a. major septal deviation
  - b. evidence of previous nasal disease or surgery
  - c. current significant nasal congestion due to common cold
13. History or presence of hypersensitivity or allergy to sufentanil or ketamine, a history of anaphylactic reactions, or a history of other allergy that, in the opinion of the investigator, contraindicates their participation.
14. Has received treatment with sufentanil and/or ketamine during the last 72 hours
15. Is currently participating in or has participated in an interventional clinical trial with an investigational compound or device in the 4 weeks prior to signing the informed consent/assent for this trial.
16. Previous enrolment in the present study.

### 3.3 Recruitment and Screening

Participants will be identified and recruited from the ED. The participant-targeted recruitment initiatives and any information given to potential participants and/or their parents or legal guardians will be submitted to, and approved by, the respective Ethics Committee(s) prior to implementation.

The Investigator is responsible for obtaining informed consent and assent (in accordance with local regulations), please see section 8.2. Information about the study may be explained to the participant and parent/guardian by an experienced study nurse but the consent should be obtained by the investigator.

During the screening assessment, a participant ID number will be assigned for identification of the participants. The Investigator will maintain a participant ID Log for all participants who undergo

Confidential

/ v 3.2/ 18-SEP-2024

screening. If assessments required for screening have already been completed as part of standard treatment at the ED prior to participant/parent/guardian signing the ICF, historical data can be collected, see section 4.2.

After completion of screening (part 1), all participants deemed eligible to take part in this study will be enrolled. If a participant screen fails, this will be noted in a screen failure form.

### 3.3.1 Pregnancy and contraceptive guidance

Females that have reached menarche, will be excluded if they verbally state any possibility of being pregnant or if they are breastfeeding.

Eligible females that have reached menarche must use contraception for 7 days after IMP administration. Acceptable contraceptive methods include:

- Sexual abstinence
- Combined hormonal (estrogen and progesterone) contraception associated with inhibition of ovulation (oral, intravaginal or transdermal)
- Progestogen-only hormonal contraception associated with inhibition of ovulation (oral, injectable or implantable)
- Intrauterine device (IUD)
- Intrauterine hormone-releasing system (IUS)
- Bilateral tubal occlusion
- Vasectomized partner

## 3.4 Lifestyle considerations

### 3.4.1 Meals and dietary restrictions

Not applicable in an emergency setting. However, the time of last oral intake (fluids and solids) will be documented.

### 3.4.2 Activity restrictions

Ambulation is allowed between drug administration and any indicated medical procedures.

### 3.4.3 Driving and bicycling

Participants will be told not to engage in critical complex personal decisions, or operate heavy machinery, car driving or riding a bicycle on the day of the IMP administration.

## 4 STUDY PROCEDURES

### 4.1 Overall Study Design

This study is an open label multi-centre study evaluating the safety, tolerability, analgesic efficacy, and feasibility of IN CT001, on acute pain relief in pediatric participants in an acute care setting where acute pain relief is judged to be needed. The study comprises of 2 study parts on Day 1, and part 3 consisting of a follow up phone call (on Day 2-7). On Day 1, participants will be screened (Part 1), enrolled and treated (Part 2). For the overall study design, see Figure 1.

[figure not shown]

Figure 1. Schematic Study Design,

ED; emergency department, IMP; investigational medicinal product.

Children and young people attending an ED who report moderate or severe pain will be eligible for enrolment in the study. In total, 150 evaluable participants will be included, with an estimated need to screen 180 subjects to reach the necessary number of evaluable patients. Each participant will receive one or potentially two consecutive doses of intranasally administered CT001 (with 10-15 min in-between).

All study related activities will take place in the acute care setting, including monitoring of vital signs (measurements of pulse rate, oxygen saturation and respiratory rate). The participating EDs will all contain appropriate equipment and drugs to address any complications from the trial medication, including standard airway/breathing life support equipment, rescue analgesia, and naloxone.

## 4.2 Clinic visits

### Part 1; Screening (Day 1)

Potentially-eligible participants and their parents or legal guardian will be provided with written information about the study. Families who state an interest in participation will be asked to provide written informed consent +/- assent, as appropriate for the age group in accordance with local legislation. A patient ID number will then be assigned.

Following completion of the informed consent form (ICF), a formal screening assessment will be conducted, including assessment of eligibility according to the study inclusion and exclusion criteria. Pain scoring within the screening assessment will be conducted using the following pain intensity scores:

Age  $\geq$ 9 years: A 0-10 numerical rating scale (NRS) scale (10).  
Age  $\geq$ 5 to  $<$ 9 years: The Wong-Bake FACES scale (14).  
Age  $\geq$ 1 to  $<$ 5 years: The FLACC scale (15).

The same pain scale will be used for all subsequent study pain scores for that patient.

Any preceding data from the routine ED triage assessment (such as demographics, injury type, pain score, concomitant medications, and vital signs) can be utilized and transferred onto the screening electronic Case Report Form (eCRF).

The screening assessment will also include documentation of participant demographics, past medical history, and concomitant medications. If not already undertaken at the routine triage assessment, the participant will be weighed. Where a participant's injury makes weighing impractical, an estimated weight will be documented.

Females participants that have reached menarche, will be asked if it is any possibility that they could be pregnant. If they respond yes, they will not be eligible for the study. Females participants that have reached menarche and who are sexually active will be asked to follow contraceptive guidance for 7 days following IMP administration.

For further guidance on assessments at screening, see Study Assessment Chart [Table 1](#).

### Part 2; Baseline and IMP treatment (Day 1)

The baseline assessment will include a repeat pain score, sedation score, and measurement of the participant's vital signs (respiratory rate, pulse rate, oxygen saturation) if not already undertaken at

the routine triage assessment. Once the pre-treatment assessments are performed the IMP will be administered.

After administration of IMP, pain scores will be assessed at the following approximate intervals (10, 15, 20, 30, 45, 60 min post IMP), as specified in the Study Assessment Chart (Table 1). The actual timepoints for pain assessment relative to IMP administration will be recorded in the eCRF.

Unscheduled pain intensity scores will be measured and documented during any potentially painful intervention (e.g. during the application of a plaster cast for a fracture), prior to rescue medication or prior to premature study withdrawal.

Where pain relief at 10-15 min after the first IMP administration is insufficient (for example, a pain score >4/10 on NRS, or at the discretion of the treating investigator), a second IMP dose of similar strength and dose can be administered to the participant. In the case of insufficient pain relief after two doses of IMP, additional analgesic medication may be administered at the discretion of the treating investigator, in accordance with standard local practice. The medication, dose and time of administration will be recorded in the eCRF.

After administration of IMP, level of sedation, vital signs (pulse rate, peripheral oxygen saturation, respiratory rate), nasal tolerability and spontaneously reported adverse events will be assessed.

Pain scores and safety assessments should continue for 60 min after the last dose of IMP, or until additional analgesic treatment or procedures need to be initiated. For further guidance on assessments at the treatment and post-treatment visit (Part 2), see Study Assessment Chart, Table 1.

Feasibility and treatment satisfaction in relation to the IMP and route of administration will be assessed prior to ED discharge.

Treatment satisfaction will be addressed by using the following standardized question: *“How satisfied are you with the study drug that you/your child received? Please think about how it helped their pain, how it was given, any side effects, and how quickly you/your child recovered”*. Respondents will answer using a 5-point Likert scale (very unsatisfied, unsatisfied, neutral, satisfied, very satisfied).

Acceptance of the intranasal route of administration will be assessed by the child. The healthcare professional will ask the child: *“If you were in this situation again and needed pain medication, would you like to receive the nasal spray (relative to getting an injection, tablet or suppositories for the pain)?* If not possible by the child, then by the parent/guardian.

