## 1.7 Ethical Considerations

### 1.7.1 Risk and inconveniences to the patients

Acute pain of moderate to severe intensity is common in children in the acute care (i.e. emergency) setting. In most cases oral treatments do not provide sufficiently rapid analgesia. Intramuscular and subcutaneous injections are also slow-acting, as well as being painful when administered. A fast titration of an effective dose within a reasonable time is also not possible. Thus, standard-of-care to date to manage acute moderate to severe pain is mainly off-label IN opioids. The IN route of administration has been well accepted in clinics and acute care settings by both children, parents, and healthcare staff due to its low invasiveness and high effectiveness.

The IMP CT001 will be administered intranasally. Both sufentanil and ketamine are well-known drugs for the treatment of acute pain (9). The doses of the IMP (CT001) have previously been shown to be effective in a clinical setting in children for procedural pain management (10).

Common dose-dependent side effects of sufentanil are nausea, vomiting, itching and sedation (1- $\geq$ 10%) (4). While for IV ketamine (in sub-anesthetic doses used for analgesia), sedation and nausea/vomiting are common side effects (5). In the completed pediatric study (PDC 01-0201, EudraCT 2009-013801-33) investigating the IN combination of sufentanil and ketamine unpleasant taste, vomiting and dizziness were the most common adverse events, see Investigators Brochure, version 5.

Study medication will be administered on one occasion, with the possibility of adding a second dose if the first dose did not result in sufficient pain relief as per investigator discretion. Pain intensity will be assessed using age-relevant pain intensity scoring scales.

During and following IN administration of the combination of study drug, non-invasive assessments of heart rate, oxygen saturation and respiratory rate will be done. A physician will be present when the IMP is administered in case of potential side effects requiring any additional treatment. During the study participation, the child and parent/legal guardian will be queried for subjective adverse

events. Furthermore, the study will focus on assessment of nasal tolerability to ensure that the IMP is not associated with local irritation of the nasal mucosa. Patients will be asked specific questions related to nasal tolerability.

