**Part 3; Text/telephonic follow-up for safety (Day 2-7)**

On day 2-7 the parent/legal guardian (or patient if aged 16 to <18) will be contacted via text message (if possible), asking if the patient has experienced any side effects following discharge from the ED. If the reply is “yes” or the person does not respond to the text, the site investigator will attempt to contact them by phone to obtain further information about these adverse events. A total of 3 attempts will be made to make telephone contact. If all attempts are unsuccessful, the patient’s General Practitioner (GP) may be contacted for any relevant follow-up information. For further guidance on assessments, see Study Assessment Chart in Table 1.

Table 1: Study Assessment Chart

Visit Number and Name	1 Screening	2 Baseline and IMP Treatment	3 Follow-up (phone)
Study day	1	1	2-7
Study Activities			
Signed Informed Consent	X		
Allocation of participant ID	X		
Inclusion/Exclusion Criteria	X		
Type of injury*	X		
Demographics*	X		
Relevant Medical and surgical history*	X		
Recent and Concomitant medication* g)	X	X	X
Weight*	X		
Peripheral oxygen saturation*		X	
Pulse rate*		X	
Respiratory rate*		X	
Sedation score a)		X	
Pain intensity assessment* b)	X	X	
Administration of IMP c)		X	
Adverse events/ Serious adverse events d)		X	X
Nasal tolerability e)		X	
Feasibility and Treatment satisfaction questions f)		X	

\* if data from assessments performed prior to ICF signature are part of normal ED procedure they can be used in the study.

- a) Sedation will be assessed immediately after pain intensity assessments using the UMMS score at baseline and at 10, 15, 20, 30, 45 and 60 min post-IMP. If a second dose of IMP is needed the sedation score will be performed at the same time points relative to the second dose.
- b) Pain assessment will be performed using age-appropriate scales and they will be performed at screening, at baseline (before IMP administration), and at 10, 15, 20, 30, 45, 60 min post IMP. If a second dose of IMP is needed, the pain assessment timepoints will continue for 60 min after last IMP or until additional analgesics or procedures needs to be initiated. Unscheduled pain assessments should be done during any potentially painful intervention (e.g. during the application of a plaster cast for a fracture), prior to rescue medication or prior to premature study withdrawal.

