### 4.3.2 Pain intensity assessments

The pain resulting from injury causing the emergency visit will be quantified. The participant will be introduced to the age-appropriate pain scale and overall pain will be assessed, with no distinction made between spontaneous pain and any procedural pain.

Immediately prior to administration of the IMP (baseline), the pain intensity will be rated using the applicable tool (see below). Subsequent pain assessments will be performed at 10, 15, 20, 30, 45, and 60 min post IMP administration. If a second dose of IMP is administered after 10-15 min, the pain assessment schedule will be reset, and pain will be measured at 10, 15, 20, 30, 45, and 60 min after the second dose of IMP, or until additional analgesics or procedures needs to be initiated.

Unscheduled pain intensity scores will be measured and recorded during any potentially painful intervention (e.g. during the application of a plaster cast for a fracture), prior to rescue medication or prior to premature study withdrawal.

Age-appropriate pain intensity assessment tools will be used:

**Age ≥9 years:** The Numerical Rating Scale (NRS) will be used. The NRS scales consists of a Likert scale, anchored with numbers 0-10, with 0 marked "No pain" and the right end (10) marked "Worst pain imaginable". The patient will state the number representing their current level of pain, and the study staff will circle the applicable number on the CRF page (see [Appendix A](#)).

**Age ≥5 to <9 years:** The visual analogue scale modified with six faces developed by Wong-Baker (Wong-Baker FACES pain rating scale) will be used. Numerical values (0, 2, 4, 6, 8, 10) are listed for each face (Wong et al, 2001, see [Appendix B](#)).

**Age 1 to <5 years:** The study investigator will provide an assessment of pain, using the FLACC scale (Merkel et al, 1997, see [Appendix C](#)).

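### No pain threshold applies at the moment of dosing, and under the section 6.1.1 wording a child already at 4 or below can count as a responder without any change

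*Combined protocol and SAP*

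**What the plan says.** **Eligibility.** Section 3.1 states that "prior to performing any study-related procedures, the following inclusion criteria must all be met". Criterion 3 asks for 5 to 10 on the NRS (9 to <18 years) or FLACC (1 to <5 years), and 6 to 10 on Wong-Baker (5 to <9 years). Under section 3.3, once screening is complete, "all participants deemed eligible to take part in this study will be enrolled". Table 1 marks the inclusion/exclusion check under Screening only. Section 4.2, Part 1, adds: "Any preceding data from the routine ED triage assessment (such as demographics, injury type, pain score, concomitant medications, and vital signs) can be utilized".

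**Baseline and dosing.** Section 4.3.2 requires a fresh score: "Immediately prior to administration of the IMP (baseline), the pain intensity will be rated using the applicable tool". Section 4.2, Part 2, then goes straight to treatment: "Once the pre-treatment assessments are performed the IMP will be administered". No minimum score is named.

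**Responder.** Three wordings are in use:
- Absolute (section 6.1.1; synopsis, statistical methods): a score of 4 or below at 15 min, and within 30 min.
- Reduction (synopsis endpoint table; section 7.4.1): pain reduced to 4 or below, relative to baseline.
- Confidence-interval sentence in 7.4.1: a pain reduction whose size is 4 or less, within 30 min.

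**Analysis.** The full analysis set (7.2) takes every dosed child, with no condition on baseline pain. Sections 7.4 and 7.4.1 make the efficacy analysis descriptive, with a 95% confidence interval for the within-30-minute proportion.

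**The concern.** The trial has no control arm, so nothing in the design separates relief that came before the dose from relief due to CT001. Pain can ease between triage and dosing, and the margin is thin. A child who just qualifies needs to drop only one step, from 5 to 4 on NRS or FLACC or from 6 to 4 on Wong-Baker, to fall below the entry criterion and into the responder range. Exclusion 14 bars prior sufentanil and ketamine but no other analgesic.

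Two things are at stake. The reported responder proportion and its interval may be too high, and the same child may be classed differently depending on which section the programmer follows. Separately, a child who no longer meets the pain criterion would receive an opioid/ketamine dose, although section 4.2 itself gives a score above 4/10 as its example of insufficient relief.

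**Working it through.** **1. The plan's own figure.** Section 7.1 gives n = 113 for a one-sided 5% test against 60% with at least 80% power. It does not name the alternative; taking the cited 71.6% as the alternative:

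n = [1.645·√(0.6·0.4) + 0.842·√(0.716·0.284)]² / 0.116² = 104.4, or 112.9 with continuity correction, hence 113. Then 113/0.75 = 150.7, against 150 stated. The sizing reproduces and is not in dispute.

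**2. The wordings applied to individual children.**

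| Baseline → later score | Absolute | Reduction, literal | Reduction, read as starting above 4 | CI sentence, literal |
|---|---|---|---|---|
| 4 → 4 | yes | no | no | unclear |
| 4 → 3, or Wong-Baker 4 → 2 | yes | yes | no | yes |
| 10 → 2 | yes | yes | yes | no |
| 10 → 9 | no | no | no | yes |

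The absolute wording counts the unchanged child. The last column cannot be what is meant.

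**3. Ceiling on the bias.** Let q be the share of dosed children at 4 or below just before dosing, r the share of them counted as responders, and p the true rate in the rest. The reported rate is (1−q)·p + q·r, so the shift is q·(r−p). The documents give no q; 2%, 5% and 10% are assumed. The ceiling is r = 1.

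| q | Rate if p = 60% | Shift | Shift if p = 71.6% | Exact 95% CI, n = 150, p = 60% |
|---|---|---|---|---|
| 0 | 60.0% | 0 | 0 | 51.7 to 67.9% (90/150) |
| 2% | 60.8% | +0.8 | +0.6 | 52.4 to 68.5% (91/150) |
| 5% | 62.0% | +2.0 | +1.4 | 53.7 to 69.8% (93/150) |
| 10% | 64.0% | +4.0 | +2.8 | 55.8 to 71.7% (96/150) |

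**4. A less extreme calculation, all inputs assumed.** Screening, baseline and one post-dose score are simulated as equally correlated normal scores rounded to 0–10, with screening at 5 or more (2,000,000 draws). The drug effect is set so that 60% of children still at 5 or more before dosing reach 4 or below.

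| Mean / SD / correlation | q | Shift, absolute | Shift, reduction (literal) | No drug: absolute | No drug: reduction |
|---|---|---|---|---|---|
| 7 / 1.5 / 0.9 | 1.8% | +0.73 | +0.72 | +0.65 | +0.02 |
| 7 / 2 / 0.8 | 5.1% | +2.00 | +1.65 | +1.65 | +0.20 |
| 6 / 2 / 0.8 | 9.9% | +3.78 | +2.32 | +3.44 | +0.26 |
| 6 / 2 / 0.7 | 12.2% | +4.24 | +1.66 | +3.71 | +0.19 |

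This uses a single post-dose score. It models neither the best reading within 30 minutes nor the 2-point Wong-Baker steps and the entry score of 6.

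**5. What a pre-dose check cannot remove.** With no drug effect, 1.2% to 8.5% of children who pass the check still score 4 or below afterwards in these four settings. That part is inherent in a single-arm design.

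**The case against.** Much of the case on the other side stands.

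- **The reduction wording.** A reader might infer that no wording excludes a low baseline. That goes too far: a reduction to 4 or below, in a trial that admits only 5 or more (6 or more on Wong-Baker), is fairly read as starting above 4. It is unstated, and it does not rescue section 6.1.1, which lacks the word.
- **The interval sentence.** It follows the correct wording in the same paragraph and is best seen as a slip, not a rival definition.
- **Triage score as baseline.** The Table 1 asterisk says that "if data from assessments performed prior to ICF signature are part of normal ED procedure they can be used in the study", and it sits on the pain row. A reader might infer that an old triage score can stand as baseline. Section 4.3.2 and Table 1 footnote b, which list screening and baseline as separate scores, largely settle that it cannot.
- **Prior opioids.** Section 1.7.1 says that "standard-of-care to date to manage acute moderate to severe pain is mainly off-label IN opioids". This describes usual care. It is not evidence that enrolled children were pre-treated.
- **Clinical judgement.** Entry is for children "following an isolated injury where immediate pain relief is judged to be needed", and a physician is present at dosing (1.7.1). An investigator may well hold the dose, but no rule says so and the analysis carries no matching condition.
- **Error rate.** Set against the 60% used for sizing (77 or more of 113), the chance of passing would rise from 4.6% to 20.7% at q = 10%. A reader might take this as the trial's false-positive rate. The documents do not support that, because no test is planned.

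Section 7 also leaves technical detail to a separate SAP. Nothing in the reviewed text settles this point.

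**Conclusion.** The point holds. The missing threshold at dosing and the mismatch between the absolute and reduction wordings are both in the text. The consequence is a possible upward bias in a descriptive proportion and its 95% interval. Its size is unknown because every share used here is assumed. The ceiling is +4.0 points at q = 10% and a true rate of 60%, beside an interval about 16 points wide (67.9 − 51.7). Under the literal reduction wording with no drug effect, the assumed settings give almost nothing (0.0 to +0.3). If judgement at the bedside works as intended, q is likely to be small. The change is still worth making: the endpoint is primary, there is no control arm, the needed score is already collected, and a child could receive a dose that the protocol's own pain criterion no longer supports.

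**What to change.** **Section 4.2, Part 2.** Add: *The IMP is given only if the pain score taken immediately before dosing is still 5 or more on NRS or FLACC, or 6 or more on Wong-Baker. Otherwise the child is not dosed, is recorded as enrolled but not treated, is replaced, and is treated per local practice.* Re-check the pain criterion only. The label of enrolled but not treated fits sections 3.3 and 7.2, under which a child is enrolled once screening is complete. Add undosed children to the replacement rule in 4.5.

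**Synopsis, 6.1.1 and 7.4.1, including the interval sentence.** Use one definition: *a responder has a baseline (immediately pre-dose) score above 4 and a score of 4 or below at the stated time.* On all three scales, above 4 is the same as meeting criterion 3. Any child dosed with a baseline of 4 or below stays in the full analysis set, is reported by number and is not counted as a responder. A sensitivity analysis leaves such children out.

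**Cost.** A few sentences and one table row, with no new measurement. Some children will not be dosed and cannot be rescreened (4.5), so one who dips briefly to 4 is lost. Dosing 150 would take about 153, 158 or 167 otherwise eligible children at q = 2%, 5% or 10% (150/0.98, 150/0.95, 150/0.90). That is within the planned 180 screened (4.1), although other screen failures draw on the same margin. If low-baseline children are dosed anyway, the rule pulls the rate down (0.95 × 60% = 57% at 5%), which is why the sensitivity analysis is needed.
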